It should be noted that per the study protocol, the smoking quit date is scheduled to occur on Session 7 of the study; however, we have found that participants sometimes wish to quit smoking earlier than is called for in the study protocol. The treatment manual, which was not designed specifically for this study, indicates that changing the quit date to occur earlier is reasonable if it's based on participant preferences. Per [name], a national VA expert in integrated smoking cessation, it is reasonable in cases in which, after strong recommendations from the therapist to stick to the recommended quit date, the participant still wishes to quit earlier than recommended to allow them to, and to make modifications to the skills acquisitions components of treatment (in accordance with the manual) and change medications to coincide with the participant's preferred quit date.

If a participant is randomized to receive CPT-C, consistent with the CPT-C protocol, smokers will focus on the cognitive processing treatment components. These sessions include writing a trauma impact statement, followed by the identification of "stuck points", problematic beliefs that are believed to interfere with recovery from PTSD. In addition, patients will complete A-B-C (Activating Event, Belief, Consequence) worksheets and Challenging Questions worksheets.

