### Assessments After Screening

Prior to each session, participants will complete questionnaires to assess psychiatric symptoms and smoking variables. These include the PTSD checklist (PCL), questions about smoking behavior in the past week, and the Beck Depression Inventory (BDI-II). In the final two sessions, participants will also complete the ASI, QOLI, TRGI, PSQI-A, CAPS, treatment satisfaction, Cook Medley Hostility Scale, e-cigarette use measure, and a question about current non-study psychotherapy. In session 8, participants will complete measures of treatment credibility and expectancy using the Reaction to Treatment Questionnaire (Borkovec & Nau, 1972). At the beginning and end of treatment, therapists will rate their level of allegiance to the therapy they are using with a single question asking "Which treatment do you think leads to better outcomes?" In the final treatment session, participants will also complete measures of SmokeFreeVet usability, and the nicotine dependence stages of change measure. In session 14 (after the final treatment session), participants will be interviewed with the CAPS.

Abstinence and relapse will be monitored by ED entries and at visits 7-14. Participants will provide breath samples for carbon monoxide (CO) analysis at every laboratory visit following their quit date. The first verification of smoking abstinence will occur on the morning following their quit date. Smoking abstinence will be obtained by self-report and verified by comparing CO levels to the level obtained at the baseline visit. The chart below lists the sliding scale of CO values that will be considered validating. At the six month follow-up visit, salivary cotinine will also be used to confirm self-reported

smoking abstinence. The formula in Table 1 below uses the participant's CO reading at the screening visit to determine the threshold that will be considered as confirming smoking abstinence after the quit date for each participant.

Table 1. Carbon Monoxide Thresholds for Validating Smoking Abstinence			
CO SCREENING	AM CO LIMIT		
		AM CO Limit after Overnight	
14-15	15	Abstinence	
16-18	16	AM CO Limit Formula: [14 + (.25 *	
19-21	17	(1.33 * (SCREENCO -14)))]	
22-24	18		
25-27	19		
28-30	20		
31-33	21		
34-36	22		
37-39	23		
40-42	24		
43-45	25		
46-48	26		
49-51	27		
52-54	28		
55-57	29		
58-60	30		
61-63	31		
64-66	32		
67	33		

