# Nicotine Replacement Therapy

All participants will receive nicotine replacement therapy in session 6, and will be asked to begin using NRT on their quit date (just prior to session 7). Participants will be provided with detailed information and education regarding the use of the nicotine skin patches. This educational component will include a rationale for using the patches, proper placement of the patch, when to use them, possible side effects, and how to report side effects to research staff as they may occur in the course of the study. All participants will also be given the option of one NRT rescue method of their choosing (nicotine gum, lozenges or inhalers).

Medications will be distributed under the consultation of study physician, [name]., Ph.D. [name] prescribes smoking cessation pharmacotherapy for the Durham VA specialty smoking cessation clinic. [name] is familiar with standard smoking cessation pharmacotherapy and side effects. He will determine initial nicotine dosage levels and consult on any adjustments to medication dosage. For example, patients only smoking 10 cigarettes a day would likely not benefit from 21mg/day nicotine patches, and will begin NRT at 14mg/day. Recent research has suggested that for heavy smokers (i.e., smokers with CO readings higher than 30 ppm), smoking cessation efficacy is greater when high dose (42 mg) nicotine patches are used in the pre-cessation phase (Rose, personal communication; Rose, 2010). The side effect profile for heavy smokers using a 42 mg patch is low. Rose (personal communication) reports that 2.5% of heavy smokers using a 42 mg. patch pre-quit report vomiting (as compared to 0.4% with the 21 mg. patch). No other adverse effects were reported. Smokers in this study were allowed to use their usual brand of cigarettes. Taken together, these studies suggest that pretreatment with nicotine patch while smoking cigarettes is safe and tolerable.

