# **Data Analysis and Hypotheses:**

The following variables will be described for the sample as a whole: minority status, marital status, age, trauma exposure, negative affect level, PTSD symptom severity, nicotine dependence, mean pack years, nicotine cigarette brand, and mean number of cigarettes smoked daily.

Because one of the aims of this study is to assess the efficacy of the combined CPT-C and smoking intervention on smoking cessation, we will analyze these variables to determine whether they change over time.

- Compared to the smoking cessation alone protocol, the smoking cessation + concurrent CPT-C protocol will result in reduced frequency and intensity of PTSD symptoms.
- Compared to the smoking cessation alone protocol, the smoking cessation + concurrent CPT-C protocol will result in reduced depressive symptoms.
- 3) The smoking cessation + concurrent CPT-C protocol will result in decreased smoking rates, relative to published data on VA smoking cessation usual care.
- 4) Greater PTSD symptom reduction during the smoking cessation + concurrent CPT-C treatment will result in longer duration to smoking lapse and relapse.
- 5) Exploratory research question: Will use of automated text messaging as an adjunct to smoking cessation be feasible, and will it impact quit rates and symptom severity?

Hypothesis 1. Compared to the PTSD Coach and smoking cessation protocol, the CPT-C and smoking cessation protocol will result in reduced frequency and intensity of PTSD symptoms. The change in PTSD symptoms over time will be analyzed using repeated-measures ANOVA, utilizing data provided at baseline, post-treatment, and 6-months post-quit. We will evaluate the potential influence of several potential psychosocial covariates on smoking abstinence, including: 1) demographics (age, race, socioeconomic

status), 2) psychiatric variables (PTSD symptom severity, depression, substance abuse/dependence), 3) smoking variables (self-efficacy, motivation to quit, social support, smokers in social group), and 4) treatment process variables (therapeutic alliance, satisfaction with treatment, attendance at sessions, homework adherence).

Hypothesis 2. Compared to the PTSD Coach and smoking cessation protocol, the CPT-C and smoking cessation protocol will result in reduced depressive symptoms. Analysis procedures for Hypothesis 2 will be the same as those used for Hypothesis 1.

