Hypothesis 3. The CPT-C and smoking cessation protocol will result in decreased smoking rates, relative to published data on VA smoking cessation usual care. An outcome variable denoting the proportion of subjects abstinent at Week-6 will be regressed on the group proxy and included covariates using standard logistic regression procedures. A secondary analysis will explore cessation rates at the 6-month follow-up.

Hypothesis 4.-The level of PTSD symptom reduction during the intervention will be related to longer latency to relapse. PTSD symptom change scores will be used to evaluate the degree of PTSD symptom reduction. We will fit Cox proportional hazard regression models to the data to evaluate effects of PTSD symptom reduction on the time to relapse.

Hypothesis 5. Exploratory research question: Will use of automated text messaging as an adjunct to smoking cessation be feasible, and will it impact quit rates and symptom severity? This will be evaluated by examining proportion of participants choosing to utilize text messaging, retention rates, and usage rates.

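### Hypothesis 4 does not require PTSD change to be measured before relapse; as baseline to post-treatment change, the predictor is completed after the event in early relapsers

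*Combined protocol and SAP*

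**What the plan says.** The Hypothesis 4 paragraph (Data Analysis and Hypotheses) has three sentences. The first states the expectation: "The level of PTSD symptom reduction during the intervention will be related to longer latency to relapse". The second gives the predictor: "PTSD symptom change scores will be used to evaluate the degree of PTSD symptom reduction". The third gives the model: "We will fit Cox proportional hazard regression models to the data to evaluate effects of PTSD symptom reduction on the time to relapse".

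Other sections bear on it:

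- **Scope.** The hypothesis lists in Objectives and in the Data Analysis section tie Hypothesis 4 to the CPT-C treatment, name both lapse and relapse, and use causal wording. The analysis paragraph covers relapse only and does not name the arm.
- **Time points.** The only PTSD time points in the analysis section belong to Hypothesis 1: "utilizing data provided at baseline, post-treatment, and 6-months post-quit".
- **Instruments.** The Screening Session section assigns PTSD symptom severity to the PCL and uses the CAPS for eligibility. Both are repeated. Assessments After Screening says "Prior to each session, participants will complete questionnaires to assess psychiatric symptoms and smoking variables", with the PCL among them, and "In session 14 (after the final treatment session), participants will be interviewed with the CAPS".
- **Quit date.** Intervention Protocol says "the smoking quit date is scheduled to occur on Session 7 of the study", and lets participants who insist quit earlier. The Nicotine Replacement Therapy section places the quit date just before session 7.
- **Relapse.** The Relapse section defines it as 5 or more cigarettes a day on 3 days running.

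**The concern.** A Cox model with a fixed covariate treats the covariate as known when follow-up starts. Here the clock most naturally starts at the quit date, when only about half of the CPT sessions have been given. A change score that ends after treatment is therefore not known at time zero, and for early relapsers it includes ratings made after the outcome.

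If relapse worsens PTSD ratings, early relapsers will show less PTSD reduction because they relapsed, and the model will read this as reduction delaying relapse. If relapse eases the ratings, the error runs the other way. Either way, the analysis could not tell the hypothesised direction from its reverse. With instrument, window and clock all open, the choice of predictor would fall to the analyst after the data are in.

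**Working it through.** **Reproduction.** The plan gives no event count, hazard ratio (HR), power or alpha for Hypothesis 4, so there is no figure to reproduce.

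**Timeline.** NRT ends 6 weeks after the quit date (Nicotine Replacement Therapy), and Table 2 puts the end of NRT at session 13. With the quit date at session 7, session 13 is about week 6. Session 14 is the 1-week post-treatment visit (Procedures), so about week 7. CPT sessions 7–12 fall at study sessions 8–13, after quitting. A session-13 PCL or session-14 CAPS is therefore taken 6–7 weeks into the risk period.

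**Share relapsed before the end score.** All inputs are assumed: 70% relapsed by week 26 and a Weibull time to relapse with shape k = 1 (constant hazard) or 0.5 (front-loaded).

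F(t) = 1 − exp{−H (t/26)^k}, with H = −ln(1 − 0.70) = 1.204.

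- k = 1, t = 6: 1 − exp(−0.278) = 24%
- k = 1, t = 7: 1 − exp(−0.324) = 28%
- k = 0.5, t = 6: 1 − exp(−0.578) = 44%
- k = 0.5, t = 7: 1 − exp(−0.625) = 46%

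**Size of the distortion.** Further assumptions: CPT-C arm of 35 (70 participants split equally; the allocation ratio is not stated) and no true effect. The observed end reduction equals the true reduction minus d SD in anyone who relapsed before the end score. Cox fits, 5% Wald test, 4000 replicates per setting, median HR per SD of reduction. Ranges cover both shapes and both end times.

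| End scores | d | HR | Type I error |
|---|---|---|---|
| All present | 0 | 0.99–1.01 | 5%–6% |
| All present | 0.3 | 0.86–0.91 | 8%–11% |
| All present | 0.5 | 0.78–0.87 | 11%–22% |
| Half of early relapsers missing | 0.3 | 0.89–0.95 | 6%–8% |
| Half of early relapsers missing | 0.5 | 0.81–0.91 | 8%–13% |

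With feedback of the opposite sign (0.3 SD), HR is 1.10–1.16.

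**Scale.** Expected events are 35 × 0.70 = 24.5, so the standard error of the log HR is about 1/√24.5 = 0.20. At d = 0.3 the shift is ln 0.91 = −0.09 to ln 0.86 = −0.15, which is below one standard error.

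**Missing end scores alone.** With d = 0 and 50% or 80% of early relapsers removed, HR is 0.98–1.01 and error 5%–6%. The cost is in events. Those remaining are 35 × {0.70 − m F}: for m = 0.5, 35 × (0.70 − 0.121) = 20.3 down to 35 × (0.70 − 0.232) = 16.4.

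**The case against.** The strongest reply is that the bias needs two things the documents do not state. The first is the baseline to post-treatment reading: a pre-quit or per-session score would also fit the words. The second is feedback from relapse to PTSD ratings; without it, error stays at 5%–6%. Both points stand, and they make the bias conditional. They do not close the gap, because nothing in the plan excludes the problematic reading, and reduction over the intervention, taken literally, runs past the quit date.

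The feedback model is also severe, since it shifts every early relapser permanently. The plan encourages renewed quit attempts. If half of early relapsers carry no shift by the end score (assumed), error falls to about 6%–7% at 0.3 SD and 7%–10% at 0.5 SD.

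Three stronger readings are tempting and are not supported:

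- **That the result is biased towards the hypothesis.** The documents give no sign for the feedback.
- **That losing relapsers biases the result by itself.** The Relapse section says everyone completes the protocol and then makes completion optional after relapse, so end scores may well be missing. Missingness that depends only on relapse costs events and power and leaves the null HR at about 1. Bias would need dropout that also depends on PTSD change, which the documents do not indicate.
- **That relapse has no data source.** Assessments After Screening names diary entries and visits 7–14, and the Relapse section adds Timeline Followback. What is missing is the rule for deriving dates. The definition needs daily counts, and the diary covers only two post-quit weeks.

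**Conclusion.** The concern holds as a specification gap with a conditional bias, and it should be fixed. Hypothesis 4 leaves open the start and end assessments, the instrument and the clock origin, and does not order the predictor before relapse. On the natural reading, everyone who relapses in the first 6–7 weeks has a predictor completed after the event: 24%–46% of the arm under the assumed relapse curves. False-positive error then runs from nominal with no feedback to 11%–22% at 0.5 SD, and is smaller if early relapsers lack end scores or have quit again.

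The relapse rate, curve shape, arm size and feedback are all assumptions, so these figures show what could happen and do not estimate what will. The ordering problem itself follows from the schedule alone.

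**What to change.** State that the Hypothesis 4 predictor uses only PTSD ratings made before the event, and start the clock at each participant's recorded actual quit date. Then:

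- **Primary model (one suitable choice).** In the CPT-C arm, as the hypothesis lists have it, fit a Cox model with the per-session PCL as a time-varying covariate, lagged one session and adjusted for screening PCL. With no true effect and no lapse before relapse, this gave HR 1.00–1.01 and error 5.1%–6.3% in simulation (arms of 25 or 35, 50%–90% relapse).
- **Simpler alternative.** Use PCL change up to the last rating before quitting. Reconcile first whether quitting comes at or just before session 7.
- **Whole-treatment change.** Use it only in a landmark analysis from session 14 among those still relapse-free, naming PCL or CAPS.
- **Lapse and dates.** Fit the same model to time to first lapse, and state how dates are taken from the diary, visit reports and Timeline Followback.

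No new data are needed, but there are costs. The figures below assume n = 35, 70% relapse and a true HR of 0.6 per SD.

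- Early risk weeks use only partial-treatment change. If the hazard follows completed reduction, power is about 41%–49% for the lagged model against 65% for whole-treatment change with all end scores (51%–55% if half of early relapsers lack one). If the hazard follows current PTSD level, it is 57% against 51%–59%.
- Pre-quit change alone has power of 35% (completed reduction) or 41%–50% (current level).
- The landmark analysis keeps 19–25 people and 7–15 events, with power of 20%–40%.
- A lapse shortly before relapse can still feed back into the lagged rating. With lapses averaging 0.5–2 weeks before relapse and 0.3–0.5 SD feedback, the null HR is 0.90–0.99 and error 6%–8%. The first-lapse model avoids this.

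At this sample size, effect sizes with confidence intervals should lead the report.
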